### Determination of Subjects for Analysis

All subjects that completed 4 weeks of elevated night pacing. Subjects that were unable to tolerate or withdrew from the treatment during the first 4 weeks because of safety or other issues will not be included in this efficacy analysis. MNLWHF questionnaire responses will only be included if at least 17 of the 21 questions are completed at baseline and 4 weeks.

### **MNLWHF Questionnaire – 8 weeks**

#### Hypothesis

There is an improvement in quality of life of an additional 4 week period of elevated night pacing after an initial 4 week period of elevated night pacing compared to that period of 4 weeks with the elevated night pacing programmed OFF after the initial 4 weeks period of elevated night pacing, as assessed by the MNLWHF questionnaire.

#### Analysis Methods

A paired comparison of the scores at the 8 week visit compared to the score at the 4 week visit period compared to the value at the start of the period will be calculated. A one-sided paired t-test will be performed testing the hypothesis

$$H_0: \mu_{ON} \leq \mu_{OFF}$$

$$H_a: \mu_{ON} > \mu_{OFF}$$

Where  $\mu_{ON}$  = difference in quality of life score from week 4 to week 8

SAS code similar to the following will be used to evaluate the effect of the study therapy on the MNLWHF endpoint between week 4 and week 8:

```
PROC TTEST;
  CLASS trt;
  VAR mnlwhfdiff;
RUN;
```

### Determination of Subjects for Analysis

All subjects that completed 4 weeks of elevated night pacing. MNLWHF scores at time of exit will be used for subjects that do not complete the full 4 weeks of participation in the

study from week 4 to week 8. MNLWHF questionnaire responses will only be included if at least 17 of the 21 questions are completed at both 4 and 8 weeks.

### **EQ-5D-5L Questionnaire – 8 weeks**

#### Hypothesis

There is an improvement in quality of life from baseline after an 8 week period of elevated night pacing, as assessed by the EQ-5D-5L Questionnaire. This assumes the effect is the same whether or not elevated night packing is turned off at week 4.

#### Analysis Methods

A paired comparison of the value at the end of the period compared to the value at the start of the period will be calculated. A one-sided paired t-test will be performed testing the hypothesis

$$H_0: \mu \leq 0$$

$$H_a: \mu > 0$$

Where  $\mu$  = difference in EQ-5D-5L score from baseline to week 8 visit

The EQ-5D-5L summary health score is calculated based on five “dimension” questions: mobility, self-care, usual activities, pain/discomfort, anxiety/depression. Each dimension has five options which are: 1=no problem, 2=slight problem, 3=moderate problem, 4=severe problem, 5=unable to perform.

SAS code similar to the following will be used to evaluate the 8 week EQ-5D-5L endpoint:

```
PROC TTEST;
  PAIRED eq5d0*eq5d8;
RUN;
```

#### Determination of Subjects for Analysis

All subjects that completed 8 weeks of elevated night pacing. Subjects that were unable to tolerate or withdrew from the treatment during the first 4 weeks because of safety or other issues will not be included in this efficacy analysis. EQ-5D-5L questionnaire responses will only be included if all 5 questions were answered at baseline and 8 weeks. EQ-5D-5L score at time of exit will be used for subjects that do not complete the full 4 weeks of participation in the study from week 4 to week 8.

## Hypothesis

There is more of an improvement in quality of life after an 8 week period of elevated night pacing than for a 4 week period of elevated night pacing followed by 4 weeks with the elevated night pacing programmed OFF after the initial 4 weeks period of elevated night pacing, as assessed by the EQ-5D-5L questionnaire.

## Analysis Methods

A paired comparison of the scores at the 8 week visit compared to the score at the baseline visit will be calculated. A one-sided paired t-test will be performed testing the hypothesis

$$H_0: \mu_{ON} \leq \mu_{OFF}$$

$$H_a: \mu_{ON} > \mu_{OFF}$$

Where  $\mu_{ON}$  = difference in EQ-5D-5L score from baseline to week 8

SAS code similar to the following will be used to evaluate the effect of the study therapy on the EQ-5D-5L endpoint between baseline and week 8:

```
PROC TTEST;
  CLASS trt;
  VAR eq5ddiff;
RUN;
```

## Determination of Subjects for Analysis

All subjects that completed 8 weeks of elevated night pacing. Subjects that were unable to tolerate or withdrew from the treatment during the first 4 weeks because of safety or other issues will not be included in this efficacy analysis. EQ-5D-5L scores at time of exit will be used for subjects that do not complete the full 4 weeks of participation in the study from week 4 to week 8. EQ-5D-5L questionnaire responses will only be included if all 5 questions were answered at baseline and 8 weeks.

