	
 
• Symptom Assessment
 
• Heart Rate
 
 
4 Week In-Clinic Follow Up Visit (Randomization):
 
 
• Medications
 
• Physical Assessment (including weight, heart rate and blood pressure)
 
• NYHA classification
 
• MN Living with Heart Failure Questionnaire
 
• 6 Minute Walk Test
 
• Blood Draw
 
• Echo
 
• Device Interrogation (initial)
 
• Save-to-Media (initial)
 
• Program the sleep function to OFF if randomization assignment is OFF (and program the pacing parameters)
 
• Device Interrogation (final) - this needs to be completed at the end of the visit after programming has been completed
 
• Save-to-Media (final)
 
• Adverse Events (report new/assess ongoing AEs), Study Deviations, System Modifications, Device Deficiencies, Crossovers (as they occur)
 
 
6 Week Telephone Call Follow Up Visit:
 
 
• Symptom Assessment
 
• Heart Rate
 
 
8 Week In-Clinic Follow Up Visit:
 
 
• Medications
 
• Physical Assessment (including weight, heart rate and blood pressure)
 
• NYHA classification
 
• MN Living with Heart Failure Questionnaire
 
• EQ-5D-5L Questionnaire
 
• 6 Minute Walk Test
 
• Blood Draw
 
• Echo
 
• Device Interrogation (initial)
 
• Save-to-Media (initial)
 
• Program the sleep function to OFF if subject still has sleep function ON (and program the pacing parameters)
 
• Device Interrogation (final) - this needs to be completed at the end of the visit after programming has been completed
 
• Save-to-Media (final)
 

--	--

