## 5.3. Study Procedures

Clinical data is collected at designated time points throughout the study as indicated in Table 1 below. Data will be collected using eCRFs, an electronic data management system for clinical studies. At the baseline, 4 week, 8 week, and 12 week visits subjects are to fill out the MN Living with Heart Failure Questionnaire and perform a 6 Minute Walk Test. At the same visits, an echocardiogram must be done, for which instructions are provided in an Echocardiography Handbook (provided under separate cover). A blood draw must also be done, (instructions are provided under separate cover.) The device programming should occur after all other study procedures are complete, except for the final device interrogation and save-to-media. The EQ-5D-5L Questionnaire will only be collected at the Baseline and 8 week visits.

In addition to eCRF data, non-eCRF data will be collected to include device interrogation files/save-to-media and digital echo data.

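### The EQ-5D-5L ON-versus-OFF comparison is restricted to subjects with a full 8 weeks of pacing, a condition no OFF-arm subject treated per protocol can meet

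*SAP*

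**What the plan says.** SAP 7.9.4 plans two EQ-5D-5L analyses at 8 weeks.

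- **Between arms.** The hypothesis sets 8 weeks of pacing against "a 4 week period of elevated night pacing followed by 4 weeks with the elevated night pacing programmed OFF". The code is a two-group t-test on the baseline-to-week-8 difference, with treatment arm as the class variable. The analysis set is "All subjects that completed 8 weeks of elevated night pacing".
- **Change from baseline.** The set is defined by the same sentence. The hypothesis adds: "This assumes the effect is the same whether or not elevated night packing is turned off at week 4".

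Protocol 14.1.4 gives both analyses the same set.

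Both SAP set definitions also carry two rules on early leavers. In the between-arm analysis, one reads "EQ-5D-5L scores at time of exit will be used for subjects that do not complete the full 4 weeks" of participation between weeks 4 and 8, and the other says that "responses will only be included if all 5 questions were answered at baseline and 8 weeks". On collection, SAP 5.3 says: "The EQ-5D-5L Questionnaire will only be collected at the Baseline and 8 week visits".

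For the 4 week visit, the protocol Synopsis instructs: "Program the sleep function to OFF if randomization assignment is OFF". Protocol Table 5 allows that visit on days 21 to 35 after Baseline and the 8 week visit on days 49 to 63.

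The other between-arm analyses over weeks 4 to 8 (NT-proBNP, troponin and LVEF in SAP 7.9.2, MNLWHF in 7.9.4, the walk test in 7.9.5, echo in 7.9.6) begin their set definition with "All subjects that completed 4 weeks of elevated night pacing".

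**The concern.** The set definition requires exactly the exposure that the OFF arm is randomised not to have. Taken literally, it removes the control group from the only between-arm EQ-5D-5L analysis. An analyst would have to depart from the written plan to run the test, after data exist.

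Two linked ambiguities change who is analysed:

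- The change-from-baseline test uses the same set, but its hypothesis makes an assumption about subjects switched off at week 4. That assumption matters only if those subjects are included.
- A subject who leaves between weeks 4 and 8 is kept by the exit-score rule and removed by the rule requiring complete answers at week 8.

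**Working it through.** The documents give no SD, effect size, power or t-test alpha for EQ-5D-5L, so there is no stated figure to reproduce. The checks are on eligibility and on sample size in SD units.

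**1. Can an OFF-arm subject qualify?** Pacing starts at Baseline and ends at the 4 week visit, at the latest on day 35 if in window.

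- Against a nominal 8 weeks: 56 − 35 = 21 days short.
- Against the earliest in-window 8 week visit: 49 − 35 = 14 days short.

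On either count no OFF-arm subject treated per protocol qualifies. Only one left on pacing, or crossed back to it, could.

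**2. Size of the between-arm sets.** Inputs: 30 subjects paced and 2:1 allocation (SAP 5.1). Assumption: 0% to 20% are lost before randomisation. The 95% CI half-width in SD units is t(0.975, n1+n2−2) × √(1/n1 + 1/n2).

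| Set | No loss | 20% lost (24 randomised) |
|---|---|---|
| As written | at most 20 v 0, undefined | at most 16 v 0, undefined |
| 4-week set | 20 v 10, half-width 0.79 SD | 16 v 8, half-width 0.90 SD |

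**3. Change from baseline to week 8.** The half-width is t(0.975, n−1)/√n.

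| Reading | No loss | 20% lost |
|---|---|---|
| ON arm only | n = 20, 0.468 SD | n = 16, 0.533 SD |
| Both arms | n = 30, 0.373 SD | n = 24, 0.422 SD |

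With no loss the ratio is 0.468/0.373 = 1.25, so the ON-only interval is about 25% wider. The two readings also answer different questions.

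**4. Subjects leaving between weeks 4 and 8.** The exit-score rule needs an EQ-5D-5L at exit, but the Early Study Exit column has none (protocol Table 4, SAP Table 1). An exit score could exist by chance, since the protocol asks for a follow-up form at early exit where applicable. Even then, the completeness rule discards it because it is not a week-8 response. The MNLWHF 8-week set in SAP 7.9.4 has the same clash: exit scores are used, but 17 of 21 items must be complete at both weeks 4 and 8.

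**5. Separate and minor: the 4-week walk-test code.** SAP 7.9.5 specifies a one-sided test of an increase from baseline to week 4. The template is `PAIRED sixminwalk0*sixminwalk4` with no side option. By standard PROC TTEST behaviour, which the documents do not describe, this forms baseline minus week 4 and prints a two-sided p-value. Illustration with n = 30 and a gain of 0.35 SD: t = 0.35 × √30 = 1.917, giving p = 0.033 one-sided as planned and p = 0.065 as printed, with a negative mean.

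**The case against.** The strongest reply is that the intent is plain. The hypothesis names both regimens and the code compares arms. The same set definition excludes withdrawals in the first 4 weeks and makes provision for exits between weeks 4 and 8, which would be idle in a set of 8-week completers. The parallel analyses all use the 4-week set. No analyst would run 20 against 0. The endpoint is ancillary in a study that disclaims power, and the 4-week safety and tolerability result is what informs whether to proceed. All of this stands, and it limits the weight of the point. It does not make the written rule correct. SAP 7.10, which lists protocol errors, names only the MNLWHF reference in the walk-test section.

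The baseline-to-week-8 conflict is partial: the first sentence of that hypothesis fits the 8-week set, and only the second pulls the other way.

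A reader might infer three stronger things that the documents do not support:

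- **The trial lacks an EQ-5D-5L control group.** It does not. OFF-arm subjects are scheduled to complete the questionnaire at Baseline and week 8; only the set definition excludes them.
- **The exit-score gap is peculiar to EQ-5D-5L.** MNLWHF, the walk test, echo and blood draw are not marked at early exit either, although their 8-week sets also call on exit values.
- **The one-sided code would produce a wrong result, or a sign error in the questionnaires.** The SAP offers its code only as a guide, the walk-test text governs, and the planned p-value can be recovered from the output by halving and checking the sign. For the questionnaires, the hypotheses pair improvement with a positive difference, so a direction of benefit is implied, although the EQ-5D-5L summary scoring is not given.

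**Conclusion.** The point holds as a wrong analysis-set definition. As written, the between-arm EQ-5D-5L comparison has at most 20 ON and 0 OFF subjects, against 20 and 10 under the set used by its parallel analyses. That no per-protocol OFF subject qualifies follows from the visit windows alone; the counts assume 30 randomised 2:1 without loss. The linked change-from-baseline test has about 20 or 30 subjects depending on the reading, with an interval about 25% wider on the smaller. The exit-score and completeness rules contradict each other in both EQ-5D-5L sets and in the MNLWHF 8-week set.

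The consequence is confined to ancillary, exploratory analyses, and the intended set is evident. It should be corrected before analysis, but it does not threaten the study. The walk-test template is a small mismatch between text and code.

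**What to change.** 1. **Between-arm EQ-5D-5L set (SAP 7.9.4).** Define it as all randomised subjects who completed the first 4 weeks of elevated night pacing, analysed by randomised arm. This matches the set in the parallel analyses. List the correction in SAP 7.10 and carry it into protocol 14.1.4 at the next revision.
2. **Baseline-to-week-8 test.** Either include both arms, as the second sentence of its hypothesis assumes, or delete that sentence and state that the test is ON-arm only.
3. **Early leavers.** In both EQ-5D-5L sets, either state that subjects without a week-8 questionnaire are missing and not imputed, consistent with SAP 7.4, or let the completeness rule accept week 8 or exit where an exit score exists. Reconcile the MNLWHF 8-week set in the same way.
4. **Walk-test template.** Align it with the one-sided text, for example `PAIRED sixminwalk4*sixminwalk0` with `SIDES=U`.

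The cost is SAP wording and one code line, with no change to data collection. Adding EQ-5D-5L at early exit would be a further option, but it means a protocol revision with IRB approval at each site (protocol 16.5), and the fix does not depend on it.

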### 7.9.5. Ancillary Efficacy Endpoint: Mobility and Activity

## 6 Minute Walk Test Distance – 4 weeks

### Hypothesis

There is an improvement in the 6 Minute Walk Test distance from baseline after a 4 week period of elevated night pacing.

### Analysis Methods

A paired comparison of the value at the end of the period compared to the value at the start of the period will be calculated. A one-sided paired t-test will be performed testing the hypothesis

$$H_0: \mu \leq 0$$

$$H_a: \mu > 0$$

Where  $\mu$  = difference in 6 Minute Walk Test distance from baseline to week 4 visit

SAS code similar to the following will be used to evaluate the 4 week 6 Minute Walk Test endpoint:

```
PROC TTEST;
  PAIRED sixminwalk0*sixminwalk4;
RUN;
```

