###### Analysis Methods

A paired comparison of the value at the end of the period compared to the value at the start of the period will be calculated. A one-sided paired t-test will be performed testing the hypothesis

$$H_0: \mu \leq 0$$

$$H_a: \mu > 0$$

Where  $\mu$  = difference in quality of life score from baseline to week 4 visit

Quality of life is assessed via the MNLWHF questionnaire by the sum of the response values of the 21 questions. If not all, but at least 17 of the questions on the questionnaire are completed, the score will be summed and normalized to a scale of 0-105, based on the number of questions answered.

SAS code similar to the following will be used to evaluate the 4 week MNLWHF endpoint:

```
PROC TTEST;  
  PAIRED mnlwhf0*mnlwhf4;  
RUN;
```

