### Analysis Methods

A paired comparison of the scores at the 8 week visit compared to the score at the 4 week visit period compared to the value at the start of the period will be calculated. A one-sided paired t-test will be performed testing the hypothesis

$$H_0: \mu_{ON} \leq \mu_{OFF}$$

$$H_a: \mu_{ON} > \mu_{OFF}$$

Where  $\mu_{ON}$  = difference in 6 Minute Hall Walk distance from week 4 to week 8 in subjects randomized to the ON arm and  $\mu_{OFF}$  = difference in 6 Minute Hall Walk distance from week 4 to week 8 in subjects randomized to the OFF arm.

SAS code similar to the following will be used to evaluate the effect of the study therapy on the 6 Minute Hall Walk endpoint between week 4 and week 8:

```
PROC TTEST;
  CLASS trt;
  VAR sixminwalkdiff;
RUN;
```

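### SAP text specifies one-sided t-tests for MNLWHF, EQ-5D-5L and 6 Minute Walk, but all six code templates are two-sided and the three paired ones subtract in the reverse order

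*SAP*

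**What the plan says.** SAP 7.9.4 and 7.9.5 contain six t-tests for which the text reads "A one-sided paired t-test will be performed testing the hypothesis". Three concern change from baseline (MNLWHF at 4 weeks, EQ-5D-5L at 8 weeks, 6 Minute Walk at 4 weeks), with alternative mu > 0. Three compare the ON and OFF arms, with alternative mu_ON > mu_OFF. Protocol 14.1.4 and 14.1.5 specify the same one-sided tests.

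For the walk test, mu is the "difference in 6 Minute Walk Test distance from baseline to week 4 visit", and the text compares the end-of-period value with the starting value. The paired code is:

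- 6 Minute Walk, 4 weeks: "PAIRED sixminwalk0*sixminwalk4"
- MNLWHF, 4 weeks: "PAIRED mnlwhf0*mnlwhf4"
- EQ-5D-5L, 8 weeks: "PAIRED eq5d0*eq5d8"

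The ON versus OFF tests are two-sample calls by `trt`, for example "VAR mnlwhfdiff" for MNLWHF and "VAR sixminwalkdiff" for the walk. None of the six calls carries a `SIDES=` option.

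The SAP describes MNLWHF as a sum of 21 responses on a 0-105 scale without saying which end is better. For EQ-5D-5L it lists the response levels, "1=no problem, 2=slight problem, 3=moderate problem, 4=severe problem, 5=unable to perform", but not how they combine into the score. SAP 7.10, which lists the corrections to the protocol's statistical section, does not mention any of this.

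**The concern.** Text and code describe different tests. The bare `PROC TTEST` form is the same one the SAP uses where its text calls for two-sided tests (7.9.2, 7.9.6, 7.9.7), so nothing in the code separates the two kinds. One-sidedness was handled elsewhere: the tolerability proportions in 7.9.1 use `ALPHA=0.1` to obtain a one-sided 95% lower bound.

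The paired calls also put baseline first, so the printed estimate and confidence interval have the opposite sign to mu. A programmer who noticed only the sidedness and added an upper-tail option would then test for a shorter walk.

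Significance at 4 and 8 weeks selects the effects for specific follow-up (SAP 4.2 and 7.9.8), so it should be clear which p-value is meant. SAP section 8 sets self-validation as the minimum for efficacy results, so a second person may not catch the mismatch.

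**Working it through.** The documents give no power, effect size, SD or alpha for these tests, so there is no planned figure to reproduce. The check compares text with code and then sizes the difference.

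**SAS conventions.** `PROC TTEST` without `SIDES=` gives a two-sided p-value. `PAIRED a*b` analyses a minus b.

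**Inputs.** n = 30 comes from SAP section 6. The 20:10 split follows from 2:1 allocation of 30 (SAP 5.1). The effect sizes (in SD of the change), the smaller samples (20 pairs; 14 vs 7) and alpha = 0.05 are illustrative assumptions.

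**p-values, paired test.** t = d × √n, with df = n − 1.

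| Observed d | n | t | By the text (upper tail) | As coded (two-sided) |
|---|---|---|---|---|
| 0.5 | 30 | 2.739 | 0.0052 | 0.0104 |
| 0.5 | 20 | 2.236 | 0.0188 | 0.0375 |
| 0.34 | 30 | 1.862 | 0.036 | 0.073 |
| −0.4 (shorter walk) | 30 | −2.191 | 0.982 | 0.037 |

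**Range of disagreement at 0.05 for both.** Critical d = t_crit/√n for paired data and t_crit × √(1/n1 + 1/n2) for two arms.

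- Paired n = 30: 1.699/√30 = 0.310; 2.045/√30 = 0.373.
- Paired n = 20: 0.387 and 0.468.
- 20 ON vs 10 OFF: √(1/20 + 1/10) = 0.387, so 1.701 × 0.387 = 0.659 and 2.048 × 0.387 = 0.793.
- 14 vs 7: 0.800 and 0.969.

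Between each pair of values the text declares significance and the code does not. If the intended level is one-sided 0.025, the favourable cut-off equals that of a two-sided 0.05 test and these bands disappear. The last row of the table remains: the coded test can call a worsening significant.

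**Sign, worked example.** Assume a mean gain of 20 m, SD of change 60 m, n = 30. Then |t| = 20/(60/√30) = 1.826.

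- Code as written: mean −20, two-sided p = 0.078.
- `SIDES=U` added, order unchanged: p = 0.961.
- Order swapped and `SIDES=U` added, as the text requires: p = 0.039.

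**Direction for the questionnaires.** Only the walk test has a direction the documents settle, because improvement is a longer distance. If a higher MNLWHF score is worse (an assumption), baseline minus later already points towards benefit, and the written alternative mu > 0 is the part that is wrong. If the EQ-5D-5L score were a plain sum of the listed levels, higher would be worse; under a score where higher means better health, the reverse holds.

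**ON versus OFF.** The three calls do not give the subtraction behind the difference variables or the order of `trt`. SAP 7.9.3 codes control as 0 and treatment as 1. If that coding carries over, the default class difference is OFF minus ON, the reverse of the written contrast.

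**The case against.** The best defence is that the text governs. Every snippet is introduced as indicative, and for the walk test the written hypothesis, comparison and alternative are complete, so an analyst has a clear instruction. That stands, and it is why this cannot be called proof that a wrong test will be run.

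Subtraction order and class order do not change a two-sided p-value. True: as coded, the effect is confined to the sign of the estimate and interval, and it reaches the p-value only if a tail is added without swapping the order.

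SAP 7.9.2 says its difference variables are the difference between the 8-week and 4-week measurements. That statement is written for the safety endpoints, gives no explicit order, and cannot cover the EQ-5D-5L variable, which runs from baseline to week 8. The 0/1 arm coding likewise comes from the adverse-event analysis, so the OFF-minus-ON point is conditional.

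The tests are ancillary, unpowered and unadjusted. The decision to proceed rests mainly on 4-week tolerability (SAP section 6), and SAP 4.2 limits its 4-week follow-up to improvements. SAP 7.9.8 and 7.9.9 also allow other measures to be explored, and section 8 permits stricter validation of results used in abstracts or presentations. All of this limits the harm. It does not remove the mismatch, and the rule in 7.9.8 asks only for significance, without requiring improvement.

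**Conclusion.** The concern holds and should be fixed. All six efficacy t-tests that the text makes one-sided are coded as two-sided, and all three paired calls reverse the sign of mu as written. For a favourable result the coded p-value is twice the one the text calls for. Whether that changes a significance call depends on an alpha the SAP does not state: at 0.05 for both, the disagreement covers gains of 0.31 to 0.37 SD with 30 pairs and 0.66 to 0.79 SD with 20 vs 10; at one-sided 0.025 against two-sided 0.05, none for gains. The reversal is clearly contrary to benefit only for the 6 Minute Walk. For MNLWHF and EQ-5D-5L the correct tail cannot be settled until the scoring direction is stated. The safety and tolerability result is unaffected.

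**What to change.** Keep the protocol's one-sided tests and, in SAP 7.9.4 and 7.9.5:

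- state alpha;
- state for each score which direction is better, and how the EQ-5D-5L score is formed;
- define every change as later minus earlier and every contrast as ON minus OFF, and write each alternative in the direction of benefit;
- make the code match: variable order (for example `PAIRED sixminwalk4*sixminwalk0`), the appropriate `SIDES=` option, explicit definitions of the difference variables, and the `trt` ordering.

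Settle the scoring direction before choosing a tail for the questionnaires. If the protocol's MNLWHF alternative proves to point the wrong way, record that in SAP 7.10.

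An acceptable alternative is to report two-sided tests with the signed estimate and 95% confidence interval, recorded in SAP 7.10 as a change from the protocol.

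The first option costs a few lines of text and code; the second adds the 7.10 entry. Neither affects data collection or sample size.
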